8.5.3. Adverse Events of Special Interest

Adverse events (AEs) of special interest include hypersensitivity, hypersensitivity-like reactions, and cardiovascular events. Hypersensitivity and hypersensitivity-like reactions will be identified using standardized MedDRA queries. Cardiovascular events will be identified using the SOCs for cardiac disorders and vascular disorders.

The overviews and summaries that are provided for all TEAEs will also be provided for the AEs of special interest. In addition, the time to onset and time to recovery will be summarized.

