7.1.1 Adverse Events of Special Interest

Adverse events of special interest include hypophosphatemia, hypersensitivity/anaphylactoid reactions, injection/infusion site reactions, and cardiovascular events. The search strategy will be identified as follows:

- TEAEs of hypophosphatemia:
 - MedDRA PT Blood phosphorus decrease
 - MedDRA PT Blood phosphorus abnormal
 - MedDRA PT Hypophosphataemia
 - MedDRA PT Hypophosphataemic rickets
 - MedDRA PT Rickets familial hypophosphataemic
- TEAEs indicative of hypersensitivity/anaphylactoid reactions:
 - SMQ Anaphylactic reaction
 - SMQ Angioedema
 - PT Hypersensitivity
- TEAEs of injection/infusion site reactions:
 - MedDRA HLT Infusion site reactions
 - MedDRA HLT Injection site reactions
 - MedDRA HLT Administration site reactions NEC
 - MedDRA PT Infusion related reaction
- Cardiovascular TEAEs:
 - Cardiovascular disorders SOC
 - Vascular disorders SOC

The AEs of special interest will be summarized as below:

- Treatment-emergent AESI by SOC and PT
- Serious treatment-emergent AESI by SOC, PT
- Serious or severe treatment-emergent AESI by SOC and PT

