9. SUMMARY OF MAJOR CHANGES IN THE PLANNED ANALYSES

Compared with the study protocol (03 December 2019 Administrative Change 1), below items are the major changes made in this SAP:

1. The LOCF imputation method was proposed for paired t-test for primary and secondary efficacy endpoints in SAP.
2. The scale defined in Division of AIDS (DAIDS) Table for Grading the Severity of Adult and Pediatric Adverse Events, Version 2.1 from March 2017 (Division of AIDS, National Institute of Allergy and Infectious Diseases, National Institutes of Health, US Department of Health and Human Services) will be used to identify abnormal clinical laboratory values instead of toxicity criteria from the National Cancer Institute Common Terminology Criteria version 5 for Adverse Events specified in the protocol.

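### Outside two SMQs (anaphylactic reaction, angioedema), the SAP flags hypersensitivity events as AESI through one preferred term only, although the protocol says standardized queries will identify them; SAP Section 9 does not mention this

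*SAP*

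**What the plan says.** Protocol 8.5.3 defines the events of special interest: "Adverse events (AEs) of special interest include hypersensitivity, hypersensitivity-like reactions, and cardiovascular events". For the first two groups it gives one method: "Hypersensitivity and hypersensitivity-like reactions will be identified using standardized MedDRA queries". It names no query and does not say whether narrow or broad scope applies.

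SAP 7.1.1 has one corresponding category, "TEAEs indicative of hypersensitivity/anaphylactoid reactions". The search has three lines: "SMQ Anaphylactic reaction", "SMQ Angioedema" and "PT Hypersensitivity". The first two are SMQs and the third is a single preferred term. No scope is given for either SMQ. The SAP also has a separate category for injection and infusion site reactions, which includes "MedDRA PT Infusion related reaction" and feeds the same AESI tables.

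SAP Section 9 compares the SAP with the protocol and says "below items are the major changes made in this SAP". It lists two items: LOCF for the paired t-tests, and DAIDS grading in place of CTCAE for laboratory values. It does not mention the AESI definitions.

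**The concern.** The protocol applies standardized queries to hypersensitivity in general and to reactions that resemble it. The SAP applies them to two specific presentations and reaches everything else through one exact term. A reaction that is neither in the anaphylactic reaction query nor in the angioedema query, and that is coded to some other term, is not flagged in this category whatever its clinical nature.

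The AESI table exists to gather reactions that may be spread over several preferred terms and organ classes. If the search is incomplete, the reader sees scattered single terms in the general tables and a lower count in the grouped one. The protocol treats hypersensitivity as worth watching: a known reaction to a component of FCM is an exclusion criterion (4.2.2), and participants are observed for at least 30 minutes after each dose (5.3). The study is small and has neither a control arm nor a DSMB, so a change of one or two participants in the AESI count would be noticed.

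**Working it through.** The documents give no figure on this point, so the main check is a comparison of texts.

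**Comparison**

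| Item | Protocol 8.5.3 | SAP 7.1.1 |
|---|---|---|
| Groups | Hypersensitivity; hypersensitivity-like reactions | One combined hypersensitivity/anaphylactoid category |
| Method | SMQs for both groups | 2 SMQs + 1 PT |
| Queries named | None | Anaphylactic reaction; Angioedema |
| Scope (narrow/broad) | Not stated | Not stated |
| Listed as a change in SAP 9 | – | No |

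**Reasoning**

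1. Two of the three SAP search lines are SMQs, so the search is query-based in part.
2. The third line would add nothing if the two SMQs already covered general hypersensitivity. Its presence suggests that the SAP authors saw a gap there and filled it with one term.
3. For events outside the two SMQs, identification in this category therefore rests on one PT. That is not identification by a standardized query, which is the protocol's method for both groups.
4. An event outside this search is not lost from the report. SAP 7.1 tabulates all TEAEs by SOC and PT, with further tables by severity, for drug-related events and for serious events. If it is coded as an infusion related reaction, it also enters the AESI tables through the other category.

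**Scale, for illustration only**

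Input: n = 36, the approximate maximum in SAP 1.3.3.

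- One missed participant changes the AESI incidence by 1/36 = 2.8 percentage points.
- The exact (Clopper-Pearson) upper 95% limit for 0/36 is 1 − 0.025^(1/36) = 9.7%. The limits for other counts come from the beta quantiles:

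| Count | Incidence | Exact 95% CI |
|---|---|---|
| 0/36 | 0% | 0 to 9.7% |
| 1/36 | 2.8% | 0.1 to 14.5% |
| 2/36 | 5.6% | 0.7 to 18.7% |

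- Suppose that reactions outside the current search occur at a true rate p per participant. The documents give no rate, so p is an assumption. The chance of at least one among 36 is 1 − (1 − p)^36:

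| Assumed p | Chance of at least one |
|---|---|
| 1% | 30% |
| 2% | 52% |
| 5% | 84% |
| 10% | 98% |

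The SAP plans no confidence interval for AESI. The intervals only show how much one or two participants matter at this sample size.

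**The case against.** The strongest reply is that the SAP does what the protocol asks. The protocol speaks of queries in the plural and names none. The SAP names two and adds a term to them, which widens the search. Protocol Section 8 leaves the complete description of methods to the SAP, Section 9.8.5 allows changes in analysis methods to be documented in a plan, and SAP Section 9 claims to list only major changes. On this view, SAP 7.1.1 fills in detail and does not depart from the protocol. The SAP's AESI set is also wider elsewhere, since it adds hypophosphatemia and injection or infusion site reactions.

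Much of this stands, and it rules out three stronger readings that a reader might infer.

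- *That hypersensitivity is searched with a single preferred term.* It is not: two SMQs stand directly above that line.
- *That the protocol requires one particular hypersensitivity SMQ.* It names no query, so adding one is a recommendation that follows the protocol's method and not its literal text.
- *That the SAP search always under-counts, or that events vanish from the safety report.* The documents do not give the content or scope of the SMQs, so no lost event is shown. An under-count can be asserted only relative to a search that includes a hypersensitivity SMQ, and any event missed from the AESI tables still appears in the general TEAE tables.

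The reply does not remove the central gap. The protocol gives one method for both groups and makes no exception, and the SAP uses something else for whatever lies outside the two SMQs. The extra AESI categories do not close that gap, apart from reactions that happen to be coded to the infusion or injection site terms.

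**Conclusion.** The point holds in a limited form. Outside the anaphylactic reaction and angioedema SMQs, the SAP flags hypersensitivity and hypersensitivity-like events in this category through one preferred term. The protocol says that SMQs will be used for both groups, the SMQ scope is not stated, and SAP Section 9 is silent.

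The possible effect is an incomplete AESI grouping, not incomplete collection of events. Each participant left out would lower the AESI incidence by 2.8 percentage points if 36 are treated, and by more if fewer are. Whether anyone would be left out depends on how events are coded and on the content and scope of the SMQs, none of which the documents give. This is a cheap improvement to the safety reporting, with no bearing on the efficacy analysis.

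**What to change.** In SAP 7.1.1, add a hypersensitivity SMQ to the hypersensitivity/anaphylactoid category. Keep the two existing SMQs and the preferred term. Adding a line, as opposed to replacing the term, makes the new search a superset, so no event that is now flagged can drop out.

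State the scope, narrow or broad, of each SMQ. If the current search is kept as a separate, narrower table, list it in SAP Section 9 as a difference from protocol 8.5.3.

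The cost is a few lines of SAP text and a rerun of the AESI flag. No new data are needed. The downside is that some less specific terms will enter the AESI table.

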1.3.3 Sample Size and Statistical Power Considerations

There were no sample size estimations for this study. The current study is a rollover for study 1VIT17044. There will be a maximum of approximately 36 participants from study 1VIT17044 who had an unsatisfactory response to oral iron or required an intervention.

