7.1 ADVERSE EVENTS

Adverse events (AEs) will be coded by System Organ Class (SOC) and Preferred Term (PT) using the Medical Dictionary for Regulatory Activities (MedDRA) dictionary. Adverse event

summaries will exclude preferred terms that describe asymptomatic serum ferritin, TSAT, and reticulocyte values (or changes). This approach is justified by the reporting of these values in efficacy summaries and is consistent with the protocol-defined reporting standards for hemoglobin/hematocrit and low iron indices. For the purposes of this study, non-serious anemia (hemoglobin or hematocrit below the normal range or worsened from baseline) or iron deficiency (iron indices below the normal range or worsened from baseline) will not be considered adverse events. Anemia or iron deficiency will be considered end points if an intervention is required.

A treatment-emergent adverse event (TEAE) is defined as an event with onset date on or after the study drug start date. Partial date TEAE classification rules refer to Section 2.3.4. Only TEAEs will be included in summary tables.

The incidence of TEAEs will be summarized as the number (percentage) of subjects with TEAEs within SOC and PT. Subjects who report the same PT on multiple occasions will be counted once for the PT: under the highest severity (severe > moderate > mild) CTCAE when summarized by severity and under the closest relationship (probably related > possibly related > unlikely related > none) to study drug when summarized by relationship. If a subject reports multiple PT for a SOC, the subject will be counted only once for that SOC. Events with unknown severity or relationship will be counted as unknown.

TEAEs will be summarized as below.

- An overview table, including number of subjects with
 - TEAEs
 - serious TEAEs
 - study drug related TEAEs
 - study drug related Serious TEAEs
 - TEAEs by severity
 - TEAEs leading to study drug discontinuation or withdrawal from study
 - TEAEs leading to death
- TEAE by SOC
- TEAE by PT
- TEAE by SOC and PT
- TEAE by SOC, PT, and Severity (CTCAE)
- Study drug related TEAEs by SOC, PT
- Serious TEAEs by SOC and PT
- Study drug related serious TEAEs by SOC and PT

- TEAEs leading to study drug discontinuation or withdrawal from study by SOC and PT
- TEAEs leading to death by SOP and PT

Unless otherwise stated, all TEAE tables will be sorted by SOC and PT in decreasing frequency of the number and percentage of subjects.

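### SAP 7.1.1 names a cardiovascular SOC where the protocol names the cardiac disorders SOC, so a literal search would under-count cardiac events in the AESI tables

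*SAP*

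**What the plan says.** Protocol 8.5.3 makes cardiovascular events one of the AESI groups and gives the retrieval rule: "Cardiovascular events will be identified using the SOCs for cardiac disorders and vascular disorders".

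SAP 7.1.1 keeps the group, ending its list of AESI with "injection/infusion site reactions, and cardiovascular events", and then sets out the search strategy for each group. For cardiovascular events the strategy has two entries, "Cardiovascular disorders SOC" and "Vascular disorders SOC". The cardiac disorders SOC appears nowhere in that section.

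SAP 7.1 states that events are coded by SOC and preferred term (PT) "using the Medical Dictionary for Regulatory Activities (MedDRA) dictionary", so the names in the search must correspond to classes in that dictionary. SAP 7.1.1 then plans three AESI tables, all by SOC and PT: all treatment-emergent AESI, serious AESI, and serious or severe AESI.

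**The concern.** The SAP list is the working specification from which the AESI tables will be programmed, and one of its two cardiovascular terms differs from the protocol's. A filter that looks for the SAP's name and finds no such class in the coded data would return vascular events only. The output would give no sign of this, since an empty cardiac section looks the same whether no child had a cardiac event or the search never asked for one.

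The protocol singled out cardiovascular events in advance for an intravenous product given as a push or a 15-minute infusion. It also requires heart rate and blood pressure before, immediately after and 30 minutes after each administration. The study has one arm, at most about 36 children and no data safety monitoring board, so the descriptive AESI tables are a main place where a reader would look for this signal. An under-count caused by the label would be an error in a pre-specified safety summary.

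**Working it through.** There is no figure in the plan to reproduce and no formula to apply. The check is a comparison of text.

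**Inputs**

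| | First class | Second class |
|---|---|---|
| Protocol 8.5.3 | cardiac disorders | vascular disorders |
| SAP 7.1.1 | cardiovascular disorders | vascular disorders |

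**Step 1: overlap.** The two lists share only vascular disorders. The protocol's cardiac class has no entry under that name in the SAP.

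**Step 2: what the SAP's first term can mean.** The protocol treats cardiac and vascular disorders as separate classes of the dictionary. If the SAP meant one combined class covering both, its second line would add nothing. The reading that gives both lines work to do, and agrees with the protocol, is that the first line should say cardiac disorders. This inference rests on the two texts alone. The documents do not reproduce the MedDRA list of classes.

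**Step 3: consequence under each way of running the search.**

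- *The term is read as cardiac disorders.* The SAP search equals the protocol search and nothing is lost.
- *The term is matched literally and no class carries that name.* An event coded to cardiac disorders meets neither cardiovascular term, and the search returns vascular events only. A child with both a cardiac and a vascular event is still counted as having a cardiovascular AESI, but the cardiac SOC and PT rows are absent. A child whose only cardiovascular event is cardiac is not counted by this search at all.

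**Step 4: where those events would still be seen.** SAP 7.1 tabulates all treatment-emergent events by SOC and PT, by severity, by relationship, by seriousness, and for discontinuation and death. Cardiac-coded events appear there whatever the AESI search does. The serious-or-severe grouping in SAP 7.1.1 has no single counterpart in that list, which has a severity table and a serious-event table but not the two combined. Other AESI searches, such as the anaphylactic reaction query, might also pick up a cardiac term. The documents do not give that query's contents, so this cannot be settled from them.

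**Step 5: size.** No cardiac event rate is given or implied, and for the study as a whole the SAP says "There were no sample size estimations for this study". The range is therefore from none to all of the cardiac-coded events, as far as the cardiovascular search is concerned.

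**The case against.** The strongest reply is that this is a drafting slip that misleads nobody. SAP section 1 says the SAP is to be read together with the protocol, and the protocol names both classes. SAP 7.1 has a comparable slip, printing SOP for SOC in one table title. A programmer who filtered on a class that returned nothing would probably notice. Cardiac events remain in the general tables, where in a study this small a cardiac row missing from the AESI table would be easy to spot. Heart rate and blood pressure are summarised separately on each dosing day. Event collection, serious adverse event reporting and the primary analysis are untouched.

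Most of that stands, and it limits the impact. It does not make the specification correct. A pre-specified search should not depend on a programmer's silent repair, and the general tables do not reproduce the AESI outputs.

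A reader might also infer three stronger things that the documents do not support:

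- *That every cardiac event is lost.* The loss depends on literal matching, is confined to the cardiovascular search, and leaves the general tables complete.
- *That SAP section 9 proves an error because it does not declare the change.* That section says "below items are the major changes made in this SAP" and lists two: the imputation rule for the paired t-tests and the laboratory grading scale. It covers only major changes. It also omits hypophosphatemia and injection or infusion site reactions, which SAP 7.1.1 adds to the protocol's AESI list. Its silence therefore cannot separate a slip from a decision.
- *That the impact is 2.8%.* That is 1/36, the weight of one child at the approximate maximum enrolment. It says nothing about how many cardiac events to expect.

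**Conclusion.** The two documents disagree on an operative safety-search rule, and the SAP's wording is most likely a slip for the cardiac disorders SOC. As written and run literally, the cardiovascular search misses events coded to cardiac disorders, and all three AESI tables would under-count them, except for any retrieved by another listed search.

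This rests on two assumptions the documents do not settle: that no class in the dictionary carries the SAP's name, and that the name is matched as printed. If either fails there may be no loss, but the text still needs to agree with the protocol. The effect is limited to descriptive AESI tabulation. The correction is worth making before lock because the affected group is pre-specified and the remedy is a single line.

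**What to change.** In SAP 7.1.1, replace "Cardiovascular disorders SOC" with Cardiac disorders SOC and keep "Vascular disorders SOC", so that the search matches protocol 8.5.3. Before database lock, compare the SOCs and PTs retrieved for each AESI group with the full list of coded treatment-emergent events, and confirm that every event coded to cardiac or vascular disorders has been captured. If a different search is in fact intended, state it with dictionary names and record the departure from the protocol in SAP section 9.

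The cost is one line of SAP text and a short programming check. It needs no new data, no protocol amendment and no change to how participants are managed. Protocol section 8 has the SAP finalised before lock, so a correction made by then is clean. One made after the tables have been seen would have to be reported as a post hoc change.

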7.2 CLINICAL LABORATORY PARAMETERS

Laboratory assessments include hematology, clinical chemistry, and iron indices:

- Hematology: Hgb, Hct, RBC, WBC, MCV, MCH, MCHC, RDW, platelets, differential

count, reticulocyte count and CHr

- Clinical chemistry: sodium, potassium, chloride, BUN, creatinine, albumin, alkaline phosphatase, total bilirubin, GGT, AST, ALT, LDH, calcium, phosphorus, glucose, bicarbonate and magnesium.
- Iron indices: serum iron, serum ferritin, and total iron binding capacity (TIBC), and percentage serum transferrin saturation (TSAT).
- Other: Serum pregnancy test

All laboratory parameters will be presented in conventional units. The actual value and mean change from baseline to each scheduled visit will be summarized using descriptive statistics for each laboratory test group above.

Time course table for serum phosphate will be constructed for subjects in safety population. Descriptive statistics of days to first value of specified CTC grade and days to return to normal will be summarized. Only the subjects with a normal serum phosphate baseline value will be included in this table.

The number and percent of subjects with treatment-emergent potentially clinically significant (PCS) laboratory values after baseline will be summarized by visit. The denominator is all subjects with normal baseline and at least one post baseline assessment in the safety population and the numerator is the number of subjects with PCS (i.e., meets Grade 3 or Grade 4 AE scale defined in Division of AIDS (DAIDS) Table for Grading the Severity of Adult and Pediatric Adverse Events, Version 2.1 from March 2017 (Division of AIDS, National Institute of Allergy and Infectious Diseases, National Institutes of Health, US Department of Health and Human Services)) at any post-baseline visit.

Shift from baseline AE grade to maximum post-baseline AE grade, and shift from baseline to the last visit in terms of AE grade will be summarized, separately.

The AE grade for Chemistry and Hematology are defined in Appendix 1.1. BUN, hematocrit, bands and iron indices do not have adverse event scales available and are not evaluated separately as possible AEs.

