1.3 SUMMARY OF THE STUDY DESIGN

1.3.1 General Study Design and Plan

This is a single arm, open-label, multi-center, multi-national, non-randomized study that will evaluate the efficacy and safety of a one course treatment with FCM in participants who had an unsatisfactory response to oral iron in study 1VIT17044.

Subjects will have an EOS Visit (Day 35) from the 1VIT17044 study to qualify for entry. Subjects will then be screened, meet all inclusion criteria, no exclusion criteria and have a baseline evaluation. Based on the successful completion of the baseline evaluations, subjects will be enrolled and will receive the first dose of FCM (Day 0). The second FCM dose should occur 7 days from the first dose. Subjects will return to the clinic 14 and 28 days post their first dose for laboratory and safety assessments, and at 35 days post the first dose, participants will return to the clinic for final safety and efficacy assessments. Once all assessments are complete the participant will exit the study.

An **unsatisfactory response** to oral iron (i.e., an increase in Hgb of <1 g/dL from baseline) will be defined as non-responders to oral iron treatment. Non-responders who continue to meet all inclusion criteria (including Hgb <11 g/dL) and none of the exclusion criteria will receive 1 course of FCM.

Table 1: Schedule of Activities

Procedures	Screening ¹ Day -7 to -1	Enrollment Visit 1, Day 0	Study Visit 2 Day 7 ± 1 day	Study Visit 3 Day 14 ± 1 day	Study Visit 4 Day 28 ± 1 day	Study Visit 5 Day 35 ± 1 day
Informed Consent / Assent	X					
Medical History	X					
Physical Exam		X				X
Inclusion/Exclusion Criteria	X	X				
IRT	X	X				X
Vital Signs	X	X	X	X	X	X
Weight	X	X				
Height	X					
Temperature		X	X			
Blood sampling for Hematology, Chemistry and Iron Indices (5.5 mL) ¹	X	X	X	X	X	X
Blood sampling for Serum Pregnancy Test (1.5 mL), if applicable	X					X
Concomitant Medications	X	X	X	X	X	X
Adverse Event Assessment		X	X	X	X	X
FCM Dosing		X	X			

1. Note that there will be a 7 ± 1 day waiting period between 1VIT17044 end of study and extension screening

2. For a full description of central laboratory assessments, refer to Protocol Section 6.4.

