2. STATISTICAL METHODS

2.1 GENERAL CONSIDERATIONS

Analysis datasets will be produced according to CDISC standards. All study-collected data will be summarized in tables or graphs. Listing will be produced when appropriate and all ICH-required listings will be produced.

Continuous variables will be summarized in terms of the number of observations (n), mean, standard deviation (SD), median, quartiles (Q1 and Q3), minimum (min), and maximum (max) values. Other descriptive statistics (e.g., coefficient of variation) may be reported when appropriate. Analysis of categorical variables will include frequency counts and percentages. Unknown and missing data may be presented as a separate category and the denominator will include unknown or missing values as appropriate. If applicable, hypothesis testing will be carried out at the two-sided $\alpha=0.05$ level unless otherwise specified; 2-sided 95% confidence intervals (CIs) will be presented, where specified.

Generally, data will be summarized by nominal visit. However, data from both unscheduled and scheduled will be used for determination of last observed value, and in worst- or best-case changes and/or shifts from baseline. Assessment windows will not be defined for the purpose of classifying measurements obtained outside scheduled assessment times.

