2.3.2 Study Day

Study Day will be calculated relative to the day of first dose (defined as Day 1).

If the assessment (or event) date falls on or after the date of first dose then

$$\text{Study Day} = \text{Assessment Date} - \text{Date of First Dose} + 1$$

If assessment date falls before the date of first dose then

$$\text{Study Day} = \text{Assessment Date} - \text{Date of First Dose}$$

In the case of adverse events or concomitant medications where the assessment date is partially or completely missing, Study Day and any corresponding durations will follow the conventions given in Section 2.3.4.

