2.3.4 Handling of Missing Data

A participant who withdraws from the study for any reason will be included in the analyses regardless of time on study. Methods for handling withdrawals and missing data will be specific to each endpoint to be analyzed. Missing data will not be imputed for descriptive statistical summaries in safety or efficacy.

For statistical inferential (paired t-tests) analyses, missing data will be imputed using last observation carried forward (LOCF) method for hemoglobin and other efficacy endpoints. e.g. for primary endpoint, hemoglobin, when Day 35 data is missing (subject has discontinued before Day 35, or measurement not taken at Day 35 though subject was not discontinued), Day 28 or last unscheduled result will be carried forward. If there is no post-baseline value observed, the worst value obtained from Day 35 of all subjects in the safety population will be used. The worst value is defined as the lowest value for hemoglobin, ferritin, TSAT and reticulocyte hemoglobin content.

Dates missing the day or both day and month of the year will adhere to the following conventions to classify TEAE and to classify prior/concomitant medications.

- A medication with a completely missing start date will be considered a prior medication. A medication with a completely missing stop date will be considered a concomitant medication.
- If complete AE onset date is missing and AE end date is on or after the first dose date then it will be counted as a treatment emergent AE (TEAE) for the study. If complete AE onset date is missing and AE end date is before the first dose date then it will not be counted as a TEAE for the study.
- If an AE or a medication has a partial missing start or stop date, the following rules will be used for imputation:
 - If year is present but month and day are missing, impute start date as January 1 of that year or first dose date if the year is the same as the year of first dose date and impute stop date as December 31 of that year.
 - If year and day are present but month is missing, impute start month as January or the month of the first dose date if the year is the same as the year of first dose date and impute stop month as December.
 - If year and month are present but day is missing, impute start date as first day of that month or first dose date if the year and month are the same as the year and month of first dose date and impute stop date as last day of that month.

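### SAP 7.2's phosphate time-to-return summary covers only children who returned to normal and states no time origin; separately, the SAP cuts promised AESI outputs without declaring it

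*SAP*

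**What the plan says.** **Phosphate table.** SAP 7.2 plans a time-course table for serum phosphate, limited to children with a normal baseline value: "Descriptive statistics of days to first value of specified CTC grade and days to return to normal will be summarized". The text does not say from when either interval runs, which grade is meant, or how a child who has not returned is shown.

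**General rules that apply to it.**
- SAP 2.3.4: "Missing data will not be imputed for descriptive statistical summaries in safety or efficacy".
- SAP 2.1 requires the number of observations with every continuous summary, and listings when appropriate.
- SAP 2.3.2 counts Study Day from the first dose, as a general convention that is not linked to this table.
- The schedule in SAP 1.3.1 puts post-baseline chemistry at Days 7, 14, 28 and 35.

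**Grading.** The phosphate table refers to a CTC grade. For potentially clinically significant values, the same section uses a value that "meets Grade 3 or Grade 4 AE scale defined in Division of AIDS (DAIDS) Table", and SAP 9 declares the move from CTCAE to DAIDS. SAP 7.2 also plans that the "shift from baseline to the last visit in terms of AE grade will be summarized, separately", and says: "The AE grade for Chemistry and Hematology are defined in Appendix 1.1". The chemistry scale in Appendix 1.1 has no phosphorus row. Phosphorus is also not among the tests that SAP 7.2 names as having no scale.

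**AESIs.** Protocol 8.5.3 commits to giving AESIs every overview and summary that TEAEs receive, plus time to onset and time to recovery. SAP 7.1.1 lists three AESI tables. SAP 9 declares two changes, LOCF and DAIDS grading, and neither concerns AESIs.

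**The concern.** Hypophosphatemia is the first AESI that the SAP lists, and this table is the only planned summary of how long low phosphate lasts. A child still low at the last sample has no return time. With no imputation and no censoring, that child drops out, and the exclusion depends on the quantity being measured because the slowest to recover are the ones removed. A reader could take a mean of about 16 days as the usual duration when most affected children had not recovered.

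The missing origin adds ambiguity. The same child can have values 7 days or more apart, depending on whether days run from the first dose or from the first low value.

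The AESI gap is a separate matter: a protocol commitment is reduced without being recorded as a change.

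**Working it through.** The plan states no figure for this point, so there is none to reproduce.

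**1. Values that scheduled visits can produce** (nominal Days 7, 14, 28, 35). Measured from the first low value: first low at Day 7 gives 7, 21 or 28 days; at Day 14 gives 14 or 21; at Day 28 gives only 7. Measured from first dose, the possible values are 14, 28 or 35. A child first low at Day 14 and normal at Day 28 scores 14 days by one origin and 28 by the other (29 if Study Day is used).

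**2. Returners-only mean.** Assumptions, not in the documents: first low value at Day 14, time counted from that sample, return read at the next scheduled visit and lasting. With exponential recovery and true median m, the share still low at t days is S(t) = 2^(−t/m). The share read as 14 days is p1 = 1 − S(14), and as 21 days p2 = S(14) − S(21). Share returned = p1 + p2, returners' mean = (14·p1 + 21·p2)/(p1 + p2), and true mean = m/ln 2.

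| m (days) | p1 | p2 | Returned | Returners' mean | True mean |
|---|---|---|---|---|---|
| 14 | 0.5000 | 0.1464 | 0.6464 | (7.000 + 3.074)/0.6464 = 15.6 | 20.2 |
| 28 | 0.2929 | 0.1125 | 0.4054 | (4.101 + 2.363)/0.4054 = 15.9 | 40.4 |
| 56 | 0.1591 | 0.0698 | 0.2289 | (2.227 + 1.466)/0.2289 = 16.1 | 80.8 |

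The returners' median is 14 days in every row. Counted from first dose, the means are 14 days longer (29.6, 29.9, 30.1) and equally flat. If 10 children were first low at Day 14 (an assumed number), about 6.5, 4.1 and 2.3 of them would supply a value.

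**3. Less variable recovery.** With Weibull shape 2, S(t) = 2^(−(t/m)²), and the same inputs, 79%, 32% and 9% return. The returners' means are 16.6, 17.6 and 17.8 days against true means of 14.9, 29.8 and 59.6. At the shortest median the summary slightly overstates duration, because returns are rounded up to the next visit.

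**4. Wider range of durations.** A simulation of 200,000 episodes per scenario assumed onset uniform over Days 0–7 and log-normal duration with log-SD 0.5, with time counted from the first low sample.

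| True median (days) | 7 | 14 | 21 | 28 | 42 | 56 | 84 |
|---|---|---|---|---|---|---|---|
| True mean | 7.9 | 15.9 | 23.8 | 31.8 | 47.7 | 63.5 | 95.3 |
| Returners' mean | 11.0 | 17.6 | 20.9 | 22.6 | 24.3 | 25.1 | 26.0 |

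The summary follows duration up to about three weeks, then flattens.

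**5. Whether another output shows persistence.**
- The n for days to return counts returners. Its shortfall from the n for days to first graded value mixes children still low with children who had no later sample.
- By-visit phosphorus summaries give each visit's distribution, not whether a given child's earlier low value resolved.
- The Grade 3–4 table counts occurrence at any visit, not persistence.
- The last-visit grade shift would serve, but Appendix 1.1 supplies no phosphate grades.

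**6. The proposed summary on the step 2 inputs.** Still low at the last scheduled sample: 35%, 59% and 77%. Kaplan-Meier median at visit dates: 14 days, not reached, not reached. These separate the three cases; the returners' means do not.

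**7. AESI outputs.** SAP 7.1 lists 1 overview + 9 tables = 10. Two have direct counterparts in SAP 7.1.1 (by SOC and PT; serious by SOC and PT). The by-SOC and by-PT counts are contained in the first. That leaves 10 − 2 − 2 = 6 absent: overview, full severity table, drug-related, drug-related serious, leading to discontinuation or withdrawal, and leading to death. Adding time to onset and time to recovery gives 8.

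**The case against.** The documents give no phosphate durations, so any size rests on assumptions. SAP 2.1 requires n, and n falls sharply as recovery slows (65% to 23% in step 2), so an alert reader has some warning. Day 35 phosphorus quartiles and minimum are planned. Protocol 6.3.5 asks for Day 35 procedures before early exit, which limits missing last samples. With at most about 36 children, a listing could show each course. The largest gaps also reflect the 35-day follow-up rather than the SAP wording: no method recovers a mean of 80.8 days from it. For AESIs, the events remain in the general TEAE tables, and the serious-or-severe table partly covers severity.

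All of this stands as mitigation. None of it states how many children remain low, and a censored estimate would at least report that the median was not reached.

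Two stronger readings are tempting. A reader might infer that protocol 6.4 and 7.1 conflict on follow-up after Day 35. They are compatible: 6.4 permits a repeat of any abnormal Day 35 result, and 7.1 asks for follow-up of those judged clinically significant. What is open is only whether such repeats enter the table. A reader might also infer that the AESI cut removes phosphate timing promised in the protocol. Protocol 8.5.3 does not name hypophosphatemia; it is an AESI only in the SAP, so the cut bears mainly on hypersensitivity and cardiovascular events.

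**Conclusion.** The point holds. Followed as written, SAP 7.2 gives a summary of returners only, tied to no origin, with no statement of how many children stay low, and no other planned output supplies that number. When recovery is slow relative to follow-up, the summary understates duration: in the exponential example the mean moves by 0.5 days (15.6 to 16.1) while the true median rises fourfold.

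A reader might infer that the table says almost nothing about duration in any circumstances. The documents do not support that. They give no durations, and under the log-normal assumption the summary tracks duration roughly up to about three weeks. The figures depend on the assumed recovery shape, on counting from the first low sample rather than true onset, and on using scheduled visits only.

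The undeclared AESI reduction is established from the text alone. Both matters concern secondary safety outputs and should be fixed; the primary endpoint is not affected.

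**What to change.** **Phosphate table (SAP 7.2)**
- State the origin of each interval, for example first dose for onset and first low value for return.
- Report n (%) ever low, n (%) returned, and n (%) still low at the last scheduled phosphate sample.
- Add a time-to-return estimate censored at that sample, interval-censored or Kaplan-Meier. If few children are affected, counts and a listing are enough.
- List repeats after Day 35 separately, since that follow-up is selective.
- Use one laboratory scale for the phosphate and shift tables, consistent with SAP 9, and add its phosphate thresholds to Appendix 1.1.

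**AESIs (SAP 7.1.1 and 9)**
- Restore the missing outputs, including time to onset and time to recovery, or declare their removal in SAP 9.
- Align the Cardiovascular disorders SOC in SAP 7.1.1 with the cardiac disorders SOC named in protocol 8.5.3.

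**Cost.** SAP wording, an appendix entry and a few more outputs; no new scheduled sampling. With at most about 36 children, and only some of them low, the median may not be estimable. Kaplan-Meier at visit dates still rounds returns up to the next visit.
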